7.4.1. Visit F1 (Day 141; Week 21; Follow-up Visit)

The Follow-up Visit should occur approximately 4 weeks after completion of the EoT visit.

At Visit F1/EoS, appropriate study site personnel should:

- Record AEs and update medications.
- Review the subject's eDiary entries.
- Confirm that the subject has recorded the date and time of their last doses of glucocorticoid and mineralocorticoid (if applicable) prior to the visit using the eDiary. If not, ask the subject to record the information.
- If the subject is a premenopausal woman, confirm that she has recorded the start date of her last menstrual period using the eDiary. If not, ask the subject to record the information.

- Record vital signs and weight.
- Perform a brief PE, with particular attention to assessing the subject for adrenal insufficiency.
- Within 30 minutes prior to administration of morning replacement glucocorticoid and mineralocorticoid (if applicable) doses, collect blood samples for hematology, chemistry, and hormones (17-OHP, P, cortisol, A4, ACTH, total testosterone, and 11-ketotestosterone).
 - For each study visit, the first hormone sample collection that is obtained at the study site should be done between 6-10 AM (06:00-10:00), as close to 8 AM (08:00) as practicable.
 - Hormones should not be collected if the subject already took their replacement glucocorticoid and/or mineralocorticoid dose that morning; instead, the sample collection should be rescheduled for the next day or as soon as is feasible.
- For female subjects of childbearing potential only, collect a urine sample and perform a urine pregnancy test.
- Ask the subject to self-administer their morning replacement glucocorticoid and mineralocorticoid (if applicable) doses.
- Ask the subject to record the time of glucocorticoid and mineralocorticoid (if applicable) administration using the eDiary.
- Collect any provisioned devices.
- Once all Visit F1 procedures have been completed, discharge the subject from the study.

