3.2 Coding Systems and Conventions

3.2.1 Definition of Baseline

In general, all values recorded at Visit T1 (Day 1) prior to the first dose will be regarded as baseline values for this study. In case no predose Visit T1 (Day 1) value was recorded (expected for ECG and for coagulation parameters), the most recent value prior to Visit T1 (Day 1) will be used as baseline value instead.

For serum or plasma 17-OHP, P, cortisol, A4, ACTH, total T, and 11-ketoT, baseline is defined as the mean of the predose value from Visit T1 (Day 1) and the most recent “0-hour” value prior to Visit T1 (Day 1), if the glucocorticoid dose was the same as at Visit T1 (Day 1) (if not the same, then only the predose Visit T1 (Day 1) value will be used).

For on-site salivary 17-OHP, P, and cortisol, baseline is defined as the mean of the predose value from Visit T1 (Day 1) and the most recent “0-hour” value prior to Visit T1, if the glucocorticoid dose was the same as at Visit T1 (if not the same, then only the predose Visit T1 value will be used). Change from baseline will be calculated for salivary 17-OHP values obtained 30 minutes before, as well as 2 hours and 4 hours after intake of the morning dose of nevanimibe HCl. For additional analyses, baseline for on-site salivary 17-OHP is further categorized by the time of sample relative to the time of the morning dose of nevanimibe HCl. Thus, baseline for the predose measurement on visits T2/T3/T4/T5 is defined for the additional analyses as above, while it is defined as the T1 sample taken 2 hours after the morning dose of nevanimibe HCl for the T2/T3/T4/T5 sample taken 2 hours after the morning dose, and defined as the T1 sample taken 4 hours after the morning dose for the T2/T3/T4/T5 sample taken 4 hours after the morning dose.

For home collection salivary 17-OHP profiles, baseline for the 8 AM (08:00), noon (12:00), 4 PM (16:00), 8 PM (20:00), and 10-11 PM (22:00-23:00) time points is defined as the value obtained for the corresponding time point at Day -8.

Except for the above-mentioned case, all values recorded after the first treatment with the study drug will be regarded as post-baseline values.

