6.3 Secondary Efficacy Endpoints

The following are secondary efficacy endpoints:

-Androstenedione, progesterone, total testosterone, and 11-ketotestosterone levels as measured at Baseline, Visit T2 (Day 29), Visit T3 (Day 57), Visit T4 (Day 85), Visit T5 (Day 113; Amendment 2) and Follow-up Visit (Day 113 (Amendment 1) or Day 141 (Amendment 2)); and change from Baseline to Visit T2 (Day 29), Visit T3 (Day 57), Visit T4 (Day 85), Visit T5 (Day 113; Amendment 2) and Follow-up Visit (Day 113 (Amendment 1) or Day 141 (Amendment 2)).

-Serum 17-OHP levels as measured at Visit T1 (Day 1), Visit T2 (Day 29), Visit T3 (Day 57), Visit T4 (Day 85), and Visit T5 (Day 113; Amendment 2) at h0, h1, h2, h3 and h4 (predose and 1-4 hours after administration of the morning replacement glucocorticoid, mineralocorticoid (if applicable), and/or study drug (if applicable) doses); and change from baseline (Visit T1 (Day 1)) to Visit T2 (Day 29), Visit T3 (Day 57), Visit T4 (Day 85), Visit T5 (Day 113; Amendment 2).

-Salivary 17-OHP levels as measured at Visit T1 (Day 1), Visit T2 (Day 29), Visit T3 (Day 57), Visit T4 (Day 85), and Visit T5 (Day 113; Amendment 2) (at time points h0, h2 and h4 (just before, 2 hours after, and 4 hours after (respectively) administration of the morning replacement glucocorticoid (if applicable), mineralocorticoid (if applicable) and/or study drug (if applicable) doses)) and change from Baseline (Visit T1 (Day 1)) to Visit T2 (Day 29), Visit T3 (Day 57), Visit T4 (Day 85), and Visit T5 (Day 113; Amendment 2).

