7.6 Evaluation of Secondary Efficacy Endpoints

All secondary variables will be evaluated for the mITT population and the PPP.

Absolute values as well as change and percentage change from baseline in androstenedione, progesterone, total testosterone, and 11-ketotestosterone (as available) as measured at Visit T2 (Day 29), Visit T3 (Day 57), Visit T4 (Day 85), Follow-up Visit (Day 113; Amendment 1) or Visit T5 (Day 113; Amendment 2) and Follow-up Visit (Day 141; Amendment 2) will be assessed descriptively using summary statistics for continuous variables. Percentage change from baseline at Day x will be calculated as $(\text{measurement at Day } x - \text{measurement at baseline}) / (\text{measurement at baseline})$. Results will be presented overall and by cohort. Levels of androstenedione, testosterone and 11-ketotestosterone will additionally be summarized by sex (male, female) and cohort (cohort 1, cohort 2).

Absolute values as well as change and percentage change from baseline in serum 17-OHP levels at Visit T1 (Day 29), Visit T2 (Day 57), Visit T3 (Day 85), Visit T5 (Day 113; Amendment 2) and Follow-up Visit (Day 113 (Amendment 1) or Day 141 (Amendment 2)) will be evaluated by cohort, nevanimibe dose and overall. For each study visit, up to five (5) samples are collected per subject at specified pre/postdose timepoints. For each study day, the sum of all values from the time series (i.e., samples at specified pre/post-dose time points) will be calculated and used for comparison with data from Visit T1. Percentage change from baseline at Day x will be calculated as $(\text{measurement at Day } x - \text{measurement at baseline}) / (\text{measurement at baseline})$. For those samples with a 17-OHP value $>30 \mu\text{g/L}$, the undiluted value received after transformation of the measurement after appropriate dilution will be used. A footnote detailing the number of samples that exceeded the measurement limit of $30 \mu\text{g/L}$ will be included.

Results will be described using summary statistics for continuous variables. 90% confidence limits will be calculated for each of the visits.

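### The serum 17-OHP visit sum in SAP 7.6 has no completeness rule and no stated denominator, and its visit list includes the one-sample Follow-up Visit, so it can show a change in either direction with no drug effect

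*SAP*

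**What the plan says.** SAP 7.6 plans absolute values, change and percentage change from baseline in serum 17-OHP by cohort, by dose and overall, with 90% confidence limits for each visit.

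- Sampling: "For each study visit, up to five (5) samples are collected per subject at specified pre/postdose timepoints".
- Summary: "the sum of all values from the time series (i.e., samples at specified pre/post-dose time points) will be calculated and used for comparison" with Visit T1 data. The text does not say that these data are the T1 total.
- Percentage change: "Percentage change from baseline at Day x will be calculated as" the difference from baseline divided by baseline. It does not say whether the measurement is the total or a single sample.
- Missing data: SAP 5.1 uses observed data and does not impute unless otherwise specified. The serum paragraph specifies nothing. The next paragraph, on saliva, limits the saliva total to subjects with all five time points.
- Baseline: for serum 17-OHP, SAP 3.2.1 says "baseline is defined as the mean of the predose value from Visit T1 (Day 1") and the most recent earlier 0-hour value. If the glucocorticoid dose differed, the T1 predose value is used alone. On-site saliva also gets a time-matched 2-hour and 4-hour T1 baseline, for additional analyses; serum does not.
- Endpoint: SAP 6.3 lists serum 17-OHP at h0 to h4 "and change from baseline (Visit T1 (Day 1)) to Visit T2 (Day 29") and later visits, without Follow-up.
- Visit list in 7.6: "Visit T1 (Day 29), Visit T2 (Day 57), Visit T3 (Day 85"), then T5 and Follow-up. T4 is absent.
- Follow-up sampling: within 30 minutes before the morning steroid doses, Protocol 7.4.1 has staff "collect blood samples for hematology, chemistry, and hormones (17-OHP, P, cortisol, A4, ACTH, total testosterone, and 11-ketotestosterone"). No postdose samples are scheduled there. The 1 to 4 hour serum samples belong to T1-T5 (T1-T4 under Amendment 1).

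**The concern.** A raw sum with no completeness rule treats an absent sample as a zero. It is comparable across visits only if the same time points are present at each, and 7.6 does not require that. Follow-up can never meet the condition, because it has one scheduled sample.

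The baseline raises a separate question. The h1-h4 samples follow the morning glucocorticoid dose, and Protocol 5.7 says the timing of that dose may affect measured 17-OHP. If the predose baseline of 3.2.1 is used for the postdose changes in 6.3, the comparison includes the glucocorticoid effect as well as any nevanimibe effect.

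The trial has no control arm, and change in adrenal steroids is a secondary objective. In SAP Appendix 1 the serum change and repeated-measurement tables (14.2.1.3 and 14.2.1.5) are listed under the primary endpoint, so readers will look at them next to the responder rate. With about 20-24 subjects split by cohort and dose, a few incomplete profiles can move a cell mean. SAP 5.4 already anticipates COVID-19-related deviations, so incomplete profiles are plausible.

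**Working it through.** The plan gives no numerical result for this analysis and no formal sample size, so there is no figure to reproduce. The check applies the SAP 7.6 formula, change = (Day x - baseline) / baseline, to a case with no drug effect: the h0-h4 profile is the same at every visit.

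**1. Missing samples, flat profile, T1 sum as denominator.** Let each sample equal c, so a full sum is 5c.

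- m samples missing at Day x: ((5 - m)c - 5c) / 5c = -m/5.
- m samples missing at T1 instead: (5c - (5 - m)c) / ((5 - m)c) = m/(5 - m).

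| Samples missing (m) | Missing at Day x | Missing at T1 |
|---|---|---|
| 0 | 0% | 0% |
| 1 | -20% | +25% |
| 2 | -40% | +67% |
| 3 | -60% | +150% |
| 4 | -80% | +400% |

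**2. Profile that falls after the morning glucocorticoid.** The documents do not give the size of this fall. Assume a linear fall of fraction f from h0 to h4, with f from 0.10 to 0.60. Relative to h0 the values are 1, 1 - 0.25f, 1 - 0.5f, 1 - 0.75f and 1 - f, so the sum is 5 - 2.5f.

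- The effect of one missing sample then depends on which one it is. At f = 0.60 the sum is 3.5; losing h0 gives -1/3.5 = -28.6%, and losing h4 gives -0.4/3.5 = -11.4%.
- Complete sums at both visits: (5 - 2.5f)/(5 - 2.5f) - 1 = 0% for every f.

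**3. Follow-up, one predose sample against a five-sample T1 sum.** Flat profile: 1/5 - 1 = -80%. With the assumed fall, 1/(5 - 2.5f) - 1 runs from 1/4.75 - 1 = -79% (f = 0.10) to 1/3.5 - 1 = -71% (f = 0.60).

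**4. Predose baseline of SAP 3.2.1 as denominator.**

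- The h4 value alone: change = -f, that is -10% to -60%.
- The mean of h0-h4: change = -f/2, that is -5% to -30%.
- The raw five-sample sum: (5 - 2.5f) - 1 = 4 - 2.5f, that is +400% for a flat profile and +250% at f = 0.60. This is a spurious rise.

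**5. From one subject to a group mean.** One subject missing one Day x sample moves the mean percentage change by -20%/n: -2.0 points at n = 10 and -0.8 at n = 24. The documents give no missing-sample rate.

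**6. Visit labels.** SAP 7.6 for serum 17-OHP pairs T1, T2 and T3 with Days 29, 57 and 85. SAP 6.3, SAP 7.5 and the schedule tables put T2, T3 and T4 on those days, and 6.3 and the schedules have T1 on Day 1. As written, T1 is both the comparator and a Day 29 result, and T4 has no result. No arithmetic follows from this.

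**The case against.** The strongest reply is that the main comparisons are sound. The responder rate and its 40% criterion use predose 17-OHP against multiples of ULN, and the predose change uses a predose baseline. Both are like for like. SAP section 7 calls all summaries exploratory, and Protocol 9.5.1.2 sets no targets for secondary endpoints. A sensible programmer would take the T1 sum as denominator, and then complete profiles cancel the glucocorticoid effect, because T1 postdose samples follow the same morning dose. SAP 6.3 can be read as a T1-matched comparison, and it leaves Follow-up out of the serum profile. In 7.6, Follow-up also serves the predose value and its change, where one sample is enough.

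Most of this stands and limits the point. It does not remove it, because 7.6 requires neither the T1 sum nor complete sets, and the saliva paragraph shows that a completeness rule was thought necessary there.

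Three stronger readings are tempting and are not supported:

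- **That the analysis is tilted toward a false fall.** The error runs both ways: samples missing at T1, or a raw sum over a predose baseline, give a false rise. The glucocorticoid artefact and the -20% per missing sample also need different denominators, so they do not add up on one statistic.
- **That the wrong visit labels help create a fall.** They contradict other sections but change no value.
- **That change from baseline is the only effect measure.** The responder rate, with its 90% interval, and summaries relative to ULN are also planned.

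**Conclusion.** The point holds for the serum profile summary in SAP 7.6, which is wrong as written and not merely short of detail. The -20%, +25% and -80% figures are changes within one subject; they assume no drug effect, a flat profile and the T1 sum as denominator. The effect on a group mean depends on how many samples are missing, which cannot be known from the documents.

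The baseline issue is conditional. It arises only if SAP 3.2.1 governs the h1-h4 changes, and its size rests on the assumed 10-60% fall. The label error is certain but is a correction of text.

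Neither the trial's success criterion nor dose titration uses this sum. It should be corrected before database lock as a secondary, descriptive matter.

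**What to change.** In SAP 7.6:

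1. State that the denominator of the change and percentage change is the T1 value of the same summary.
2. Compute the sum only when all five time points are available at both visits, or replace it with the plain mean over time points present at both visits. Either gives 0% under no effect for any profile. The first loses subjects; the second keeps them but averages over different time points in different subjects. An AUC over 0-4 hours would need an extra rule when h0 or h4 is missing.
3. Restrict Follow-up to the predose value against the predose baseline, and bring 6.3 into line.
4. Correct the labels to T2 Day 29, T3 Day 57, T4 Day 85 and T5 Day 113.

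In SAP 3.2.1, add a time-matched T1 baseline for serum h1-h4, as the SAP does for on-site saliva in its additional analyses. State the downside: T1 h1-h4 follow the first nevanimibe dose, so this baseline removes glucocorticoid timing but is not fully drug-free.

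The cost is SAP wording and matching table programs. No new data are needed.

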3.3. Efficacy Assessment

Efficacy will be assessed by changes in adrenal steroids and steroid intermediates. The percentage of subjects achieving serum 17-OHP targets will serve as the primary endpoint, as this adrenal steroid intermediate is used diagnostically and to aid in the management of exogenous glucocorticoid replacement therapy in clinical practice. However, absolute target values for 17-OHP or androgens do not currently exist in treatment guidelines put forth by any of the medical societies. The entry criterion for 17-OHP is set at $\geq 4x$ ULN (for menstruating women, this criterion is adjusted for the menstrual cycle phase), which is intended to enroll subjects who are not optimally controlled while on exogenous glucocorticoid replacement therapy. The primary endpoint is aligned with the clinical goal of achieving a mildly elevated 17-OHP level, which for this study is defined as serum 17-OHP $\leq 2x$ ULN. However, salivary 17-OHP and other key efficacy parameters in the androgen pathway (i.e., androstenedione, testosterone, and 11-ketotestosterone) will also serve to define efficacy.

ACTH levels will be assessed to determine potential effects on the hypothalamic-pituitary-adrenal (HPA) axis. Glucocorticoid replacement doses must be stable for at least 4 weeks prior to starting study drug, and are expected to remain unchanged during the treatment period (except, for example, for emergency, stress dose requirements), so no significant changes in ACTH are

anticipated. Confirmation of stable ACTH levels associated with decreases in 17-OHP and androgens will help to establish the pharmacodynamic effects of nevanimibe.

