^f A salivary 17-OHP profile should be collected by the subjects on Days -8, 22, 50, and 78. These samples should be obtained at approximately 8 AM (08:00), noon (12:00), 4 PM (16:00), 8 PM (20:00), and 10-11 PM (22:00-23:00). At Visits T1, T2, T3, and T4, saliva samples for 17-OHP will be collected at the study site at approximately 8 AM (08:00), 10 AM (10:00), and noon (12:00). The 8 AM (8:00) sample should be collected prior to the subjects' morning dose of GC and MC (if applicable) and will also be assessed for P (in premenopausal women only) and cortisol. The timing of the 8 AM (08:00), 10 AM (10:00) (if applicable), and noon (12:00) samples should be adjusted to correspond to just before, 2 hours after, and 4 hours after (respectively) administration of the morning replacement glucocorticoid, mineralocorticoid (if applicable) and/or study drug (if applicable) doses.

^g On the days marked, a pregnancy test will be done on female subjects of childbearing potential only. A serum pregnancy test will be done at Screening; a urine pregnancy test will be done at Visit S2 (if applicable), B1, T1, T2, T3, T4/EoT, and F1/EoS. The start date of the subject's last menstrual period will be obtained for premenopausal women only.

^h Subjects will use the eDiary to record their glucocorticoid and mineralocorticoid (if applicable) doses (and, for premenopausal women, start dates of menstrual periods) from B1 to F1, and will also record their study drug doses from T1 to T4. The eDiary may also be used to provide reminders to subjects.

ⁱ Subjects with a 17-OHP level from Visit S1 < 4x ULN (Cohort 2) and a daily maintenance GC dose \geq the equivalent of 12 mg hydrocortisone/m² body surface area will be contacted approximately 2 weeks after Visit S1 to have their GC dose decreased by the equivalent of approximately 5 mg hydrocortisone or 1 mg prednisone or prednisolone. They will then return for Visit S2 at least 2 weeks later. If their 17-OHP level from Visit S2 is \geq 4x ULN, they will enter the Baseline period; if not, the case should be discussed with the Medical Monitor.

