- ^e For each study visit, the first blood and saliva hormone sample should be collected in the morning prior to the subjects' morning dose of GC and MC (if applicable) replacement, as close to 8 AM (08:00) as practicable and between the hours of 6-10 AM (06:00-10:00). For Cohort 2 subjects who undergo GC dose adjustment, results from the serum 17-OHP samples obtained during Screening and Baseline will be used to assess stability of 17-OHP. Cohort 2 subjects who undergo GC dose adjustment, whose subsequent serum 17-OHP results during Screening and Baseline do not indicate stable levels, should be discussed with the Medical Monitor (see Appendix 2). At Visits T1, T2, T3, T4, and T5/EoT, blood sample collections for 17-OHP will also occur approximately 1, 2, 3, and 4 hours after administration of the morning replacement glucocorticoid, mineralocorticoid (if applicable) and/or study drug (if applicable) doses.
- ^f A salivary 17-OHP profile should be collected by the subjects on Days -8, 22, 50, 78, and 106. These samples should be obtained at approximately 8 AM (08:00), noon (12:00), 4 PM (16:00), 8 PM (20:00), and 10-11 PM (22:00-23:00). At Visits T1, T2, T3, T4, and T5, saliva samples for 17-OHP will be collected at the study site at approximately 8 AM (08:00), 10 AM (10:00), and noon (12:00). The 8 AM (8:00) sample should be collected prior to the subjects' morning dose of GC and MC (if applicable) and will also be assessed for P (in premenopausal women only) and cortisol. The timing of the 8 AM (08:00), 10 AM (10:00) (if applicable), and noon (12:00) samples should be adjusted to correspond to just before, 2 hours after, and 4 hours after (respectively) administration of the morning replacement glucocorticoid, mineralocorticoid (if applicable) and/or study drug (if applicable) doses.
- ^g On the days marked, a pregnancy test will be done on female subjects of childbearing potential only. A serum pregnancy test will be done at Screening; a urine pregnancy test will be done at Visit S2 (if applicable), B1, T1, T2, T3, T4, T5/EoT, and F1/EoS. The start date of the subject's last menstrual period will be obtained for premenopausal women only.
- ^h Subjects will use the eDiary to record their glucocorticoid and mineralocorticoid (if applicable) doses (and, for premenopausal women, start dates of menstrual periods) from B1 to F1, and will also record their study drug doses from T1 to T5. The eDiary may also be used to provide reminders to subjects.

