Change and percentage change from Baseline (Visit T1 (Day 1)) in salivary 17-OHP levels (samples collected on-site) at Visit T2 (Day 29), Visit T3 (Day 57), Visit T4 (Day 85), and Visit T5 (Day 113; Amendment 2) will be evaluated by cohort, nevanimibe dose and overall. For each sampling day, up to five (5) different time points are collected per subject. Summary statistics for each time point will be calculated for each sampling day and used for comparison with data from Visit T1. In addition, for the five (5) on-site salivary samplings, the sum of the h0, h1, h2, h3 and h4 values per subject per study day will be evaluated by cohort, nevanimibe dose and overall, for all subjects with data available at all five timepoints for the respective on-site sampling day. Availability of data for imputation of the missing values will be assessed during the final DRM meeting prior to data analysis, and changes may be made to the described analysis to utilize all available data more effectively. Results will be described using summary statistics for continuous variables.

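### The SAP sets a Day -8 baseline for the home salivary 17-OHP profile, but no SAP endpoint, method or table uses it, and the on-site salivary paragraph does not match its own sampling schedule

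*SAP*

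**What the plan says.** **Collection.** The schedule footnotes in SAP 2.3 state, for Amendment 2: "A salivary 17-OHP profile should be collected by the subjects on Days -8, 22, 50, 78, and 106". For Amendment 1 they state: "A salivary 17-OHP profile should be collected by the subjects on Days -8, 22, 50, and 78". Each home profile has five clock times, from 08:00 to 22:00-23:00. The same footnotes place on-site saliva at about 08:00, 10:00 and noon, that is, predose and 2 and 4 hours after the morning dose.

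**Baseline.** SAP 3.2.1 covers the home samples explicitly: "For home collection salivary 17-OHP profiles, baseline for the 8 AM (08:00), noon (12:00), 4 PM (16:00), 8 PM (20:00") and the late-evening sample each have a baseline, which "is defined as the value obtained for the corresponding time point at Day -8".

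**Endpoint.** SAP 6.3 lists "Salivary 17-OHP levels as measured at Visit T1 (Day 1), Visit T2 (Day 29") and the later site visits, at h0, h2 and h4. It does not name the home collection days.

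**Method.** SAP 7.6 describes change from Visit T1 "in salivary 17-OHP levels (samples collected on-site) at Visit T2 (Day 29), Visit T3 (Day 57), Visit T4 (Day 85") and T5. It then speaks of as many as five time points per sampling day, and of a per-subject sum of h0, h1, h2, h3 and h4 for subjects with all five on-site values.

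**Outputs and declared changes.** SAP Appendix 1 has one salivary 17-OHP efficacy table, organised by visit, and one listing. SAP section 8 declares a single change from the protocol, to the per-protocol population.

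**Protocol.** Section 3.3 gives saliva a role in efficacy: "However, salivary 17-OHP and other key efficacy parameters in the androgen pathway" are to help define it. Section 9.5.1.2 leaves the secondary endpoints to the SAP. Section 9.5.2.1 commits to descriptive summaries of the steroids, intermediates and other hormones measured, by value and by change from baseline, for every time point, by dose, by cohort and overall. Protocol Table 3 includes salivary 17-OHP among the laboratory tests.

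**The concern.** A baseline has no purpose unless something is compared with it. Here the baseline is specified to the clock time, yet every later step (endpoint, method, table) is tied to site visits. A programmer following the SAP would have no instruction to summarise the home data.

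At stake is what the trial can say about 17-OHP across the day. The primary endpoint is a predose morning serum value that meets the target at any one visit. Serum sampling and on-site saliva both stop 4 hours after the morning dose. Protocol 5.7 itself notes that the timing of glucocorticoid replacement may affect measured 17-OHP, so a morning window does not stand in for the afternoon and evening. An analysis of the home profile added after database lock would have to be reported as not planned in advance, under the SAP's own rule in Appendix 1.

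**Working it through.** The documents state no figure on this point. The check is a text trace, a count of scheduled samples and a comparison of sampling times.

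**1. Does any step use the Day -8 baseline?**

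| SAP section | Sampling covered | Comparator |
|---|---|---|
| 3.2.1 | Home, five clock times | Day -8, same clock time |
| 6.3 | Visits T1-T5, h0/h2/h4 | Visit T1 |
| 7.6 | On-site samples | Visit T1 |
| Appendix 1 | One salivary 17-OHP table, by visit | - |
| 8 | No entry on saliva | - |

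Home Days 22, 50, 78 and 106 appear only in the schedule tables and their footnotes.

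**2. How many samples are affected?** Inputs are the schedule footnotes in SAP 2.3 and the 20-24 subjects in SAP 2.9.
- Amendment 2, home: 5 days × 5 samples = 25 per subject. On-site: 5 visits × 3 = 15. Home share: 25/40 = 62.5%.
- Amendment 1, home: 4 × 5 = 20 per subject. On-site: 4 × 3 = 12. Home share: 20/32 = 62.5%.
- Counting the single Visit B1 saliva sample as well, the shares are 25/41 = 61.0% and 20/33 = 60.6%.
- Lower end: 20 subjects × 20 = 400 (all under Amendment 1). Upper end: 24 × 25 = 600 (all under Amendment 2). The documents do not give the mix of amendments, so this is a range.

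Protocol 6.11 names only T1-T4 for on-site saliva. The schedule footnotes and the Visit T5 instructions include T5, so five visits are used here.

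**3. What do the home samples add?** On-site saliva spans 4 hours (about 08:00 to 12:00) and serum runs from h0 to h4. The home profile spans 14 to 15 hours (08:00 to 22:00-23:00). The 16:00, 20:00 and 22:00-23:00 points are three of the five samples on each home day and are scheduled nowhere else. They amount to 3 × 4 × 20 = 240 up to 3 × 5 × 24 = 360 samples.

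**4. Can the h0 to h4 sum in SAP 7.6 be computed?** It needs five on-site saliva values per day. Three are scheduled (h0, h2, h4). Under the schedule no subject has h1 or h3, so no subject qualifies. The hourly h0 to h4 pattern is the serum schedule in SAP 6.3. The SAP's only daily summary of saliva therefore cannot be produced as written.

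**The case against.** The best counter-argument is that an analysis is planned but badly worded. On-site saliva has three time points and the home profile has five, so the reference in SAP 7.6 to as many as five time points per sampling day may be meant for the home data, with the following sentence then turning to the on-site samplings. Protocol 9.5.2.1, read broadly, also covers home saliva, and SAP section 8 withdraws nothing. Appendix 1 says its titles are not binding, and the mock tables are separate documents.

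This has force. A reader might infer that the trial has no planned analysis of the home profile at all, and the documents do not support that: the protocol's general promise stands. What stands against the counter-argument is that the SAP 7.6 paragraph opens with an on-site restriction and compares with Visit T1, not Day -8. At best the text contradicts itself.

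Other stronger readings also fail:
- *The home data are cleaner because on-site post-dose samples follow a first higher dose.* This is not so at T5, nor for responders kept on their dose at T3 or T4. On-site predose samples are drawn before that visit's dose change. The 7 days between the telephone deadline and the home profile (for example Day 43 to Day 50) are target days, subject to a ±2-day window.
- *The trial aims to show control through the evening.* No objective says so. The protocol's wording on sustained decreases follows a rationale about continuous dosing over weeks.
- *The samples are already assayed.* The documents show only that collection and testing are planned.

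It is also fair to say that SAP section 7 makes all summaries exploratory and that the secondary endpoints have no targets. The success rule is untouched.

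**Conclusion.** The point holds in this form: the SAP specifies a baseline for the home profile and no endpoint, method or table that uses it. Its restriction of the salivary analysis to on-site samples narrows protocol 9.5.2.1 without a declaration in section 8. Separately, the five-value on-site sum cannot be computed from the scheduled samples.

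The size is 400 to 600 scheduled samples, about 61% to 62.5% of scheduled salivary 17-OHP samples from baseline to end of treatment. These include all 17-OHP values later in the day than about 4 hours after the morning dose. The count assumes 20-24 subjects, full collection and an unknown mix of amendments; a figure of 500 to 600 would require every subject to be under Amendment 2.

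The change is worth making before database lock. It does not affect the primary endpoint or the 40% success rule. Whether the omission is deliberate or an oversight cannot be told from the documents.

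**What to change.** Amend the SAP before final database lock.

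1. **SAP 6.3 and 7.6.** Add a descriptive secondary analysis of the home salivary 17-OHP profile: value and change from the Day -8 baseline at each clock time, plus one daily summary, at Days 22, 50, 78 and, for Amendment 2, 106. Present it by cohort, by the dose in force that day and overall, with 90% limits. A time-weighted mean is one reasonable daily summary; the choice is the sponsor's, but it should be fixed in advance with a rule for missing samples.
2. **SAP Appendix 1.** Add the matching table.
3. **SAP 7.6, on-site paragraph.** Correct the time points and the daily sum to h0, h2 and h4.
4. **If the sponsor prefers only to list the home data,** say so in section 8 with the reason.

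No extra glucocorticoid condition on the Day -8 baseline seems needed, because inclusion criterion 6 already requires a stable regimen for 4 weeks before Visit T1.

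The cost is SAP wording and one more exploratory table. Some home samples will be missing, so the number of subjects contributing at each clock time should be shown. No new sampling is required.
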